8.6. Pharmacokinetic Analysis

Plasma concentration of study drug will be provided by the central laboratory, and the plasma concentration data will be analyzed by the CRO MOSIM in the enterprise version WinNonlin software using non-compartmental model to calculate the pharmacokinetic parameters and reported independently. Analysis details are presented in the PK Statistical Analysis Report.

8.7. Pharmacodynamic Analysis

Detailed listings of pharmacodynamic markers and pSMAD2/3 in PBMCs (peripheral single cells) and TGF- β measured at each visit will be provided.

9. INTERIM ANALYSIS

No formal interim analysis is planned.

11. ATTACHMENT

NA.

12. APPENDIX I

Laboratory Test Category	Laboratory test indicators	Altered (increased/decreased)	CTCAE Grade	Criteria for judgment
Blood biochemistry	Aspartate aminotransferase (AST)	Increased	1	ULN < value $\leq 3.0 \text{ x}$ ULN (baseline normal) or 1.5 x baseline value \leq value $\leq 3.0 \text{ x}$ baseline value (baseline abnormal)
			2	$3.0 \text{ xULN} < \text{value} \leq 5.0 $ xULN (baseline normal) or 3.0 times baseline value $< \text{value} \leq 5.0 $ times baseline value (baseline abnormal)

Laboratory Test Category	Laboratory test indicators	Altered (increased/decreased)	CTCAE Grade	Criteria for judgment
			3	5.0 xULN < value ≤ 20.0 xULN (baseline normal) or 5.0-fold baseline value ≤ 20.0-fold baseline value (baseline abnormal)
			4	Value > 20.0 xULN (normal baseline) or value > 20.0 x baseline (abnormal baseline)
	Alanine aminotransferase (ALT)	Increased	1	ULN < value $\leq 3.0 \text{ x}$ ULN (baseline normal) or 1.5 x baseline value \leq value $\leq 3.0 \text{ x}$ baseline value (baseline abnormal)
			2	$3.0 \text{ xULN} < \text{value} \leq 5.0 $ xULN (baseline normal) or 3.0 times baseline value $< \text{value} \leq 5.0 $ times baseline value (baseline abnormal)
			3	5.0 xULN < value ≤ 20.0 xULN (baseline normal); 5.0-fold baseline value < value ≤ 20.0-fold baseline value (baseline abnormal)
			4	Value > 20.0 xULN (normal baseline) or value > 20.0 x baseline (abnormal baseline)
	Alkaline phosphatase (ALP)	Increased	1	ULN < value ≤ 2.5 xULN (baseline normal) or 2.0 times baseline value \leq value ≤ 2.5

Laboratory Test Category	Laboratory test indicators	Altered (increased/decreased)	CTCAE Grade	Criteria for judgment
				times baseline value (baseline abnormal)
			2	$2.5 \text{ xULN} < \text{value} \le 5.0$ xULN (baseline normal) or $2.5 \text{ times baseline}$ $\text{value} < \text{value} \le 5.0$ $\text{times baseline value}$ (baseline abnormal)
			3	5.0 xULN < value ≤ 20.0 xULN (baseline normal) or 5.0-fold baseline value ≤ 20.0-fold baseline value (baseline abnormal)
			4	Value > 20.0 xULN (normal baseline) or value > 20.0 x baseline (abnormal baseline)
	Glutamyl transpeptidase (GGT)	Increased	1	ULN < value ≤ 2.5 xULN (baseline normal) or 2.0 times baseline value \leq value ≤ 2.5 times baseline value (baseline abnormal)
			2	2.5 xULN < value ≤ 5.0 xULN (baseline normal) or 2.5 times baseline value < value ≤ 5.0 times baseline value (baseline abnormal)
			3	5.0 xULN < value ≤ 20.0 xULN (baseline normal) or 5.0-fold baseline value ≤ 20.0-fold baseline value (baseline abnormal)

Laboratory Test Category	Laboratory test indicators	Altered (increased/decreased)	CTCAE Grade	Criteria for judgment
			4	Value > 20.0 xULN (normal baseline) or value > 20.0 x baseline (abnormal baseline)
	Serum creatinine (CREA)	Increased	1	ULN < value ≤ 1.5 xULN
			2	1.5 xULN < value ≤ 3.0 xULN or 1.5 times baseline value < value ≤ 3.0 times baseline value
			3	$3.0 \text{ xULN} < \text{value} \le 6.0$ xULN or value > 3.0 baseline
			4	Value > 6.0 xULN
	Albumin (ALB)	Decreased	1	$3 \text{ g/dL} \leq \text{value} < \text{LLN or}$ $30 \text{ g/L} \leq \text{value} < \text{LLN}$
			2	$2 \text{ g/dL} \leq \text{value} < 3 \text{ g/dL}$ or $20 \text{ g/L} \leq \text{value} < 30 \text{ g/L}$
			3	Values < 2 g/dL or values < 20 g/L
	Total bilirubin (TBIL)	Increased		ULN < value ≤ 1.5 xULN (baseline normal) or 1 x baseline value < value ≤ 1.5 x baseline
			1	value (baseline abnormal) 1.5 xULN < value ≤ 3.0 xULN (baseline normal) or 1.5 times baseline
			2	value < value ≤ 3.0 times baseline value (baseline abnormal)

Laboratory Test Category	Laboratory test indicators	Altered (increased/decreased)	CTCAE Grade	Criteria for judgment
			3	3.0 xULN < value ≤ 10.0 xULN (baseline normal) or 3.0 times baseline value < value ≤ 10.0 times baseline value (baseline abnormal)
			4	Value > 10.0 xULN (normal baseline) or value > 10.0 times baseline value (abnormal baseline)
	Creatine kinase (CK)	Increased	1	ULN < value ≤ 2.5 xULN
			2	$2.5 \text{ xULN} < \text{value} \le 5.0$ xULN
			3	$5.0 \text{ xULN} < \text{value} \le 10.0 \text{ xULN}$
			4	Value > 10.0 xULN
	Total cholesterol (TCHO)	Increased	1	ULN < value ≤ 300 mg/dL or ULN < value ≤ 7.75 mmol/L
			2	$300 \text{ mg/dL} < \text{value} \le$ 400 mg/dL or 7.75 $\text{mmol/L} < \text{value} \le 10.34$ mmol/L
			2	$400 \text{ mg/dL} < \text{value} \le$ $500 \text{ mg/dL or } 10.34$ $\text{mmol/L} < \text{value} \le 12.92$ mmol/L
			3	Value > 500 mg/dL or value > 12.92 mmol/L
	Triglycerides (TG)	Increased	1	1.71 mmol/L ≤ value < 3.42 mmol/L or 150

Laboratory Test Category	Laboratory test indicators	Altered (increased/decreased)	CTCAE Grade	Criteria for judgment
				$mg/dL \le value \le 300$ mg/dL
			2	$3.42 \text{ mmol/L} \le \text{value} \le 5.7 \text{ mmol/L or } 3.00 \text{ mg/dL} \le \text{value} \le 500 \text{ mg/dL}$
			3	$5.7 \text{ mmol/L} \leqslant \text{value} < 11.4 \text{ mmol/L or } 5.00 \text{ mg/dL} \leqslant \text{value} < 1000 \text{ mg/dL}$
			4	Value > 11.4 mmol/L or value > 1000 mg/dL
	Blood glucose	Decreased	1	$3. 0 \text{ mmol/L} \leq \text{value} < \text{LLN or } 5.5 \text{ mg/dL} \leq \text{value} < \text{LLN}$
			2	2 . 2 mmol/L \leq value \leq 3 . 0 mmol/L or 4 0 mg/dL \leq value \leq 5 5 mg/dL
			3	$\begin{array}{l} 1.7 \text{ mmol/L} \leqslant \text{value} < \\ 2.2 \text{ mmol/L or } 3.0 \\ \text{mg/dL} \leqslant \text{value} < 40 \\ \text{mg/dL} \end{array}$
			4	Value < 1 . 7 mmol/L or Value < 30 mg/dL
	Calcium	Increased	1	ULN < value ≤ 2.9 mmol/L or ULN < value ≤ 11.5 mg/dL
				2.9 mmol/L < value ≤ 3.1 mmol/L or 11.5 mg/dL < value ≤ 12.5
			2	mg/dL water = 12.5

Laboratory Test Category	Laboratory test indicators	Altered (increased/decreased)	CTCAE Grade	Criteria for judgment
			3	$3.1 \text{ mmol/L} < \text{value} \le 3.4 $ mmol/L or 12.5 mg/dL < $\text{value} \le 13.5 \text{ mg/dL}$
			4	Value > 3.4 mmol/L or Value > 13.5 mg/dL
		Decreased	1	$2.0 \text{ mmol/L} \leqslant \text{value} < \text{LLN or } 8.0 \text{ mg/dL} \leqslant \text{value} < \text{LLN}$
			2	$1.75 \text{ mmol/L} \leq \text{value} < 2.0 \text{ mmol/L or } 7.0 \text{ mg/dL} \leq \text{value} < 8.0 \text{ mg/dL}$
			3	$1.5 \text{ mmol/L} \le \text{value} < 1.75 \text{ mmol/L or } 6.0 \text{ mg/dL} \le \text{value} < 7.0 \text{ mg/dL}$
			4	Value < 1.5 mmol/L or Value < 6. 0 mg/dL
	Sodium	Increased	1	ULN < value ≤ 150 mmol/L
			2	150 mmol/L < value ≤ 155 mmol/L
			3	155 mmol/L < value ≤ 160 mmol/L
			4	Value > 160 mmol/L
		Decreased	1	$130 \text{ mmol/L} \leqslant \text{value} < \text{LLN}$
			3	$120 \text{ mmol/L} \leqslant \text{value} \leqslant 130 \text{ mmol/L}$
			4	Value < 120 mmol/L

Laboratory Test Category	Laboratory test indicators	Altered (increased/decreased)	CTCAE Grade	Criteria for judgment
	Potassium	Increased	1	ULN < value ≤ 5.5 mmol/L
			2	5.5 mmol/L < value ≤ 6.0 mmol/L
			3	6.0 mmol/L < value ≤ 7.0 mmol/L
			4	Value > 7.0 mmol/L
		Decreased	1	$3.0 \text{ mmol/L} \leqslant \text{value} < \text{LLN}$
			3	2.5 mmol/L ≤ value < 3.0 mmol/L
			4	Value < 2.5 mmol/L
Blood routine	Eosinophil (EO) count	Increased	1	Value > ULN and value > baseline
	Hemoglobin concentration (HGB)	Increased	1	$ ULN < value \le ULN + 2 $ g/d L
			2	$ULN + 20 g/L < value \le ULN + 40 g/L$
			3	Value > ULN + 40 g/L
		Decreased	1	$100 \text{ g/L} \le \text{value} < \text{LLN}$ or $10 \cdot 0 \text{ g/dL} \le \text{value} < \text{LLN or } 6 \cdot 2 \text{ mmol/L} \le \text{value} < \text{LLN}$
			2	$8 \ 0 \ g/L \le value < 100$ $g/L \ or \ 8. \ 0 \ g/dL \le value$ $< 10 \ . \ 0 \ g/dL \ or \ 4.9$ $mmol/L \le value < 6.2$ mmol/L

Laboratory Test Category	Laboratory test indicators	Altered (increased/decreased)	CTCAE Grade	Criteria for judgment
			3	Value < 80 g/L or value < 8. 0 g/dL or value < 4.9 mmol/dL
	Lymphocyte (LY) count	Increased	2	$20,000/\text{mm}^{3} \le \text{value} < 4000/\text{mm}^{3} \text{ or } 20 - < 4 \text{ x} $ $10^{9}/\text{L}$
			3	Value > $20,000/\text{mm}^3$ or > $20 \times 10^9/\text{L}$
		Decreased	1	$800/\text{mm}^{3} \leq \text{value} < \text{LLN or} < \text{LLN - } 0.8 \times 10^{9}/\text{L}$
			2	$500/\text{mm}^{3} \le \text{value} < 800/\text{mm}^{3} \text{ or } < 0.8 - 0.5 \text{ x} $ $10^{9}/\text{L}$
			3	$200/\text{mm}^{3} \le \text{value} < 500/\text{mm}^{3} \text{ or } < 0.5 - 0.2 \text{ x} $ $10^{9}/\text{L}$
			4	Value < 200/mm ³ or < 0.2 x 10 ⁹ /L
	Neutrophil count (ANC)	Decreased	1	$1.5 \times 10^{9}/L \le \text{value} < \text{LLN or } 1500/\text{mm}^{3} \le \text{value} < \text{LLN}$
			2	1.0 x 10 9 /L \leq value $<$ 1.5 x 10 9 /L or 1 000/mm 3 \leq value $<$ 1 500/mm 3
			3	$0.5 \times 10^{9}/L \le \text{value} < 1.0 \times 10^{9}/L \text{ or } 500/\text{mm}^{3} \le \text{value} < 1000/\text{mm}^{3}$
			4	Value $< 0.5 \times 10^{9}/L$ or Value $< 5.00/mm^{3}$

				_
Laboratory Test Category	Laboratory test indicators	Altered (increased/decreased)	CTCAE Grade	Criteria for judgment
	Platelet count (PLT)	Decreased	1	75.0×10^{9} /L \leq value \leq LLN or 75000 /mm $^{3} \leq$ value \leq LLN
			2	$50.0 \times 10^{9}/L \le \text{value} < 75.0 \times 10^{9}/L \text{ or } 5 0000/\text{mm}^{3} \le \text{value} < 75000/\text{mm}^{3}$
			3	$25.0 \times 10^{9}/L \le \text{value} < 50.0 \times 10^{9}/L \text{ or } 2 $ $5000/\text{mm}^{3} \le \text{value} < 50000/\text{mm}^{3}$
			4	Value < 25.0 x 10 ⁹ /L or value < 2 5000/mm ³
	White blood cell count (WBC)	Decreased	1	$3.0 \times 10^{9}/L \le \text{value} < \text{LLN or } 3 000/\text{mm} ^3 \le \text{value} < \text{LLN}$
			2	$2.0 \times 10^{9}/L \le \text{value} < 3.0 \times 10^{9}/L \text{ or } 2000/\text{mm}$ $^{3} \le \text{value} < 3000/\text{mm}$
			3	$1.0 \times 10^{9}/L \le \text{value} < 2.0 \times 10^{9}/L \text{ or } 1000/\text{mm}$ $^{3} \le \text{value} < 2000/\text{mm}$
			4	Value $< 1.0 \times 10^{9}/L$ or value $< 1.000/mm^{3}$
Coagulation function	Activated partial thromboplastin time (APTT)	Increased	1	ULN < value ≤ 1.5 xULN
			2	$1.5 \text{ xULN} < \text{value} \le 2.5 $ xULN
			3	Value > 2.5 xULN

Laboratory Test Category	Laboratory test indicators	Altered (increased/decreased)		Criteria for judgment
	International normalized ratio (INR)	Increased	1	$1.2 < \text{value} \le 1.5$
			2	$1.5 < \text{value} \le 2.5$
			3	Value > 2.5
Urine routine	Urine protein	Increased	1	1 +
			2	2+, 3+
			3	4 +

Note: LLN means lower limit of normal; ULN means upper limit of normal.

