8.4.2. Laboratory Evaluations

By-visit descriptive summary will be provided for hematology, blood biochemistry, urinalysis (quantitative measurements), coagulation, thyroid function, and their changes from baseline.

For hematology, blood biochemistry, coagulation, and cardiac markers, changes in CTCAE grade from baseline (Grade 0 to 4, where Grade 0 is non-missing value other than Grade 1-4) to worst CTCAE grade after treatment starts (Grade 0 to 4, where Grade 0 means normal) will be summarized using shift tables. Test results from both scheduled and unscheduled visits will be included. For the tests without corresponding CTCAE grades, results in shift tables will be categorized into "lower than normal values and higher than normal values (i.e., both higher than normal values and lower than normal values occurred after first dose of treatment)", "lower than normal values", "normal values", and "higher than normal values". CTCAE grading reference ranges for laboratory tests are detailed in Appendix I.

Qualitative descriptive summaries will be provided for urinalysis (qualitative) results measured at each visit. A shift table will also be provided by normal, abnormal without clinical significance, and abnormal with clinical significance. For urine protein, a shift table by CTCAE grade will also be provided.

Laboratory test results will be listed separately for hematology, urinalysis, coagulation, blood biochemistry, virology, thyroid function, cardiac markers, and pregnancy test.

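### SAP Appendix I omits the measured value from the Grade 3 abnormal-baseline criterion for AST, ALP and GGT; programmed as printed, it grades every such subject 3 or higher

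*SAP*

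**What the plan says.** SAP section 8.4.2 summarizes blood biochemistry by CTCAE grade, from the baseline grade "to worst CTCAE grade after treatment starts (Grade 0 to 4, where Grade 0 means normal) will be summarized using shift tables", and refers to Appendix I for the grading limits.

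In Appendix I each liver enzyme has two sets of limits: multiples of the ULN when baseline is normal, and multiples of baseline when it is abnormal. The Grade 3 cells for AST, ALP and GGT give the normal-baseline half in full: "5.0 xULN < value ≤ 20.0 xULN (baseline normal". The abnormal-baseline half of the same three cells reads "5.0-fold baseline value ≤ 20.0-fold baseline value (baseline abnormal". The matching half of the ALT cell reads "5.0-fold baseline value < value ≤ 20.0-fold baseline value (baseline abnormal". Above it, Grade 4 for a subject with an abnormal baseline is "value > 20.0 x baseline (abnormal baseline". Below it, Grade 2 ends at 5.0 times baseline for all three tests.

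For decreased hemoglobin, one of the three alternative Grade 3 limits is "value < 4.9 mmol/dL", while the Grade 2 range in the same unit family starts at 4.9 mmol/L.

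**The concern.** A grading rule has to refer to the result being graded. This one does not: it sets two multiples of the same baseline against each other. Appendix I is the operative reference for the shift tables, so the cells are instructions to a programmer and not background text.

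Safety and tolerability are a primary objective (SAP section 2). The tumor types named for expansion in section 3 include hepatocellular carcinoma and cholangiocarcinoma/gallbladder cancer, where abnormal liver tests at entry are plausible, although the SAP gives no frequency. If the rule were coded as it stands, the AST, ALP and GGT shift tables would show Grade 3 in subjects whose values had not moved. If the same limb were also used to grade the baseline value, those subjects would start at Grade 3 and genuine rises to Grade 1 or 2 would be hidden.

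**Working it through.** The plan gives no figure to reproduce. The check applies the printed rules to example values.

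**Inputs from Appendix I, abnormal-baseline limits, as multiples of baseline b**

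| Test | Grade 1 | Grade 2 | Grade 3 as printed | Grade 4 |
|---|---|---|---|---|
| AST | 1.5 to 3.0 | above 3.0 to 5.0 | 5.0b ≤ 20.0b | above 20.0 |
| ALP, GGT | 2.0 to 2.5 | above 2.5 to 5.0 | 5.0b ≤ 20.0b | above 20.0 |
| ALT (for comparison) | 1.5 to 3.0 | above 3.0 to 5.0 | 5.0b < value ≤ 20.0b | above 20.0 |

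**Step 1. The printed condition.** Dividing 5.0b ≤ 20.0b by b gives 5 ≤ 20 for any b > 0. It is always true, whatever the post-dose result.

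**Step 2. Worked example for AST.** Assumed, not in the SAP: ULN 40 U/L and baseline 60 U/L, so baseline is abnormal. Where more than one grade is met, the highest is kept. A dash means that no grade from 1 to 4 is met.

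| Post-dose value (U/L) | Value / baseline | Grade as printed | Grade with the ALT wording |
|---|---|---|---|
| 60 | 60/60 = 1.0 | 3 | – |
| 100 | 100/60 = 1.67 | 3 | 1 |
| 240 | 240/60 = 4.0 | 3 | 2 |
| 450 | 450/60 = 7.5 | 3 | 3 |
| 900 | 900/60 = 15 | 3 | 3 |
| 1300 | 1300/60 = 21.7 | 4 | 4 |

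The two rules agree only above 5 times baseline. At or below that, the printed rule gives Grade 3 where the ALT wording gives no grade, Grade 1 or Grade 2.

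**Step 3. ALP and GGT.** The pattern is the same with their own lower limits. As printed, ratios of 1.0, 2.4, 4 and 10 are all Grade 3 and 25 is Grade 4. With the measured value restored they are no grade, 1, 2, 3 and 4.

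**Step 4. Does restoring the value close the scale?** Yes. Grade 2 ends at 5.0b, Grade 3 runs from above 5.0b to 20.0b and Grade 4 starts above 20.0b, with no gap or overlap.

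**Step 5. Extent.** Five liver tests have baseline-relative limits: AST, ALT, ALP, GGT and total bilirubin. Three are affected. The normal-baseline halves are complete in all five.

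**Step 6. Hemoglobin.** 4.9 mmol/dL × 10 dL/L = 49 mmol/L. Appendix I pairs 80 g/L with 4.9 mmol/L, so the printed limit corresponds to 10 × 80 = 800 g/L, a level that any hemoglobin result would be below. The other two alternatives in the cell, 80 g/L and 8.0 g/dL, agree with Grade 2.

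**The case against.** The strongest reply is that the omission corrects itself. The ALT row, the complete half of the same cell, the end of Grade 2 and the start of Grade 4 leave only one sensible rule, and a competent programmer would notice that the condition contains no patient result. The tables are descriptive, no hypothesis is tested, and the by-visit summaries and laboratory listings do not depend on the grade. All of this stands and limits the size of the point. It does not remove the need to correct a rule that the tables rely on.

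Part of Appendix I is garbled in the text of the PDF, so a reading fault cannot be wholly excluded. The same omission in three separate cells, with ALT intact, makes that unlikely. For the single hemoglobin cell the doubt is greater.

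Three stronger inferences are tempting but are not supported:

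- **That the criterion might be met by nobody, so that values between 5 and 20 times baseline fall to Grade 0.** The literal text is always true. Only a decision to discard the limb would leave those values ungraded. Even then, the catch-all in section 8.4.2, "where Grade 0 is non-missing value other than Grade 1-4", defines Grade 0 at baseline. After treatment starts, Grade 0 means normal, which such values are not.
- **That the tables will certainly be wrong.** That depends on how the cells are programmed, which the SAP does not show.
- **That Grade 3 liver toxicity is miscounted throughout.** Section 4.1.1 grades AE severity by CTCAE v5.0, and section 8.4.2 cites Appendix I only for laboratory tests.

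**Conclusion.** The point holds as a drafting error in an operative rule, limited in reach and easily corrected. As printed, the Grade 3 abnormal-baseline criterion for AST, ALP and GGT is satisfied by every subject with a positive baseline. Programmed that way, each baseline-abnormal subject is at least Grade 3 in those three shift tables. ALT, total bilirubin, normal-baseline subjects and the AE and DLT tables are unaffected.

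This rests on two assumptions: that the cells are coded literally, and that the highest grade met is the one kept. A program that stopped at the first grade met would give a different pattern, but an unchanged abnormal value would still be Grade 3. The number of subjects affected cannot be given, because the SAP does not state how many enter with abnormal enzymes.

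The hemoglobin unit is a secondary point and matters only if results are held in mmol units.

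**What to change.** In Appendix I, restate the abnormal-baseline half of Grade 3 for AST, ALP and GGT as 5.0 × baseline value < value ≤ 20.0 × baseline value, matching ALT. Confirm that the grading programs use this rule, and if tables have already been produced, check those three tests in baseline-abnormal subjects. Reconcile the unit of the third hemoglobin Grade 3 alternative with the Grade 2 limit of 4.9 mmol/L.

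The cost is an edit to four cells and a program check. No new data are needed, and no analysis outside these shift tables changes.

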8. STATISTICAL METHOD

8.1. General Statistical Consideration

The statistical analysis plan be finalized prior to data base lock. All analyses and data presentations will be generated using SAS® Version 9.4 or higher software

Descriptive summary

Continuous variables: Descriptive statistics will include the number of non-missing values (n), arithmetic mean, standard deviation (SD), median, minimum and maximum values.

The minimum and maximum values will be displayed to the same decimal precision as the source data, the arithmetic mean and median values will be displayed to one more decimal than the source data, and the SD value will be displayed to two more decimals than the source data for the specific variable.

Categorical variables: Descriptive statistics will include counts and percentages per category. The denominator in all percentage calculations will be the number of participants in the relevant analysis set, unless otherwise specified. Percentages will be displayed to one decimal place with the following exceptions: 1) percentages will not be displayed for zero frequencies; 2) percentages will be displayed as "100%" when percentage is 100%.

ORR and DCR will be calculated, the corresponding two-sided 90% confidence intervals will be estimated by the Clopper-Pearson method.

Baseline

Baseline is defined as the last non-missing measurement collected on or before first study drug administration. For ECGs, the average of the ECG parameters should be used.

Censor rule

Table 3 below shows the censor rule for PFS:

Table 3 Censor rule for PFS

No.	Situation	Event or Censor / Analyais date
1	PD or death	Event / PD date or death date
2	Have at least one post-baseline assessment, no PD, no Death	Censor / Last imaging date
3	No post-baseline assessment and no Death	Censo r/ First dosing date

Only subjects with the BOR of CR or PR will be included for DOR analysis. DOR will apply the same consor rule as PFS.

Best overall response (BOR) is the best measured response at any time post treatment. Subject without any post-treatment assessments will be treated as non-responder.

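### Three printed rules behind the laboratory shift tables do not work: an empty lymphocyte Grade 2, a repeated cholesterol grade, and two meanings of Grade 0

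*SAP*

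**What the plan says.** Section 8.4.2 plans shift tables from the baseline grade to the worst grade after treatment starts, for haematology, biochemistry, coagulation and cardiac markers. It refers to Appendix I for the grading limits.

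- **Lymphocytes, increased (Appendix I).** The Grade 2 row reads "20,000/\text{mm}^{3} \le \text{value} < 4000/\text{mm}^{3", and its version in 10^9/L has the same order (20, then below 4). The Grade 3 row reads "Value > $20,000/\text{mm}^3$ or > $20 \times 10^9/\text{L". There is no Grade 1 row.
- **Total cholesterol (Appendix I).** Four adjoining bands rise from ULN through 300, 400 and 500 mg/dL. They are labelled 1, 2, 2 and 3. The top band, labelled Grade 3, is "Value > 500 mg/dL or value > 12.92 mmol/L".
- **Grade 0 (8.4.2).** On the baseline axis: "where Grade 0 is non-missing value other than Grade 1-4". On the post-treatment axis: "Grade 0 to 4, where Grade 0 means normal".
- **Fallback (8.4.2).** Low, normal and high categories exist only for ungraded tests: "For the tests without corresponding CTCAE grades, results in shift tables will be categorized into".

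**The concern.** A programmer will code Appendix I as printed. Doing so leaves raised lymphocyte counts without an increased grade and puts two cholesterol bands that the appendix itself separates under one grade. It also treats the same abnormal, ungraded value differently on the two axes of one table. Safety is a primary objective of this trial (section 2), and these tables are part of how it is reported. An error in them can hide an abnormality or leave a subject without a cell.

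**Working it through.** **1. Lymphocytes, increased.** Inputs: the Grade 2 and Grade 3 rows of Appendix I. As printed, Grade 2 requires value >= 20,000 and value < 4,000. The lower bound exceeds the upper bound, so the interval is empty. The form in 10^9/L fails in the same way.

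| Count (/mm3) | As printed | Grade 2 as 4,000 < value <= 20,000 |
|---|---|---|
| 4,000 | none | none |
| 4,001 | none | 2 |
| 10,000 | none | 2 |
| 20,000 | none | 2 |
| 20,001 | 3 | 3 |

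The gap covers 20,000 - 4,001 + 1 = 16,000 whole-number counts. Grade 3 begins strictly above 20,000, so the upper end of Grade 2 must include 20,000 if no gap is to remain.

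**2. Total cholesterol.** Inputs: the four bands and their labels.

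| Value (mg/dL) | Band | Printed grade | Grade if numbered in sequence |
|---|---|---|---|
| 350 | 300-400 | 2 | 2 |
| 450 | 400-500 | 2 | 3 |
| 550 | above 500 | 3 | 4 |

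Every value still gets exactly one grade, so nothing is stranded here. The last column is an illustration only, because CTCAE v5.0 itself is not among the documents. Appendix I has 23 tests, 5 of them graded in both directions (calcium, sodium, potassium, haemoglobin, lymphocytes), which makes 23 + 5 = 28 scales. Cholesterol is the only one with a repeated label.

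**3. Grade 0.** The two definitions agree unless a value is abnormal and meets no grade. Such values exist under Appendix I:

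- *WBC.* The row "White blood cell count (WBC") is graded only as decreased. A count of 15 x 10^9/L (assumed above ULN) is Grade 0 at baseline. After treatment it is neither graded nor normal.
- *AST with an abnormal baseline.* Grade 1 starts at 1.5 x baseline. With a baseline of 4 x ULN, a later 5.6 x ULN is 5.6 / 4 = 1.4 x baseline. It meets no grade but is not normal.

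The low/normal/high fallback does not help, because these tests do have CTCAE grades.

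The width of the ungraded zone above ULN depends on the baseline. The SAP gives no eligibility limits, so the baselines below are assumed:

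| Assumed abnormal baseline (x ULN) | AST/ALT: below 1.5 x baseline | ALP/GGT: below 2.0 x baseline | Bilirubin: up to 1.0 x baseline |
|---|---|---|---|
| 1.2 | 1.8 x ULN | 2.4 x ULN | 1.2 x ULN |
| 2 | 3.0 x ULN | 4.0 x ULN | 2.0 x ULN |
| 3 | 4.5 x ULN | 6.0 x ULN | 3.0 x ULN |

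The same problem arises for high values of the five tests graded only as decreased (albumin, glucose, neutrophils, platelets, WBC), for low values on increase-only scales such as CK and creatinine, and for eosinophils above ULN but not above baseline.

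*From value to subject.* The table uses each subject's worst post-treatment grade. Take the AST baseline of 4 x ULN and these invented courses:

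- 5.6 then 4.0 x ULN: ratios 1.4 and 1.0, nothing graded or normal, so no valid cell.
- 5.6 then 0.9 x ULN: the second value is normal, so Grade 0.
- 5.6 then 8 x ULN: 8 / 4 = 2.0 x baseline, so Grade 1.

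Only the first subject is left without a category.

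**The case against.** **Extraction damage.** The empty interval rests on the direction of the inequality signs, and some nearby rows (calcium Grade 2, triglycerides) show signs garbled in conversion from PDF. Descending bounds with the opposite signs would be valid. This cannot be excluded, but several signs in two units would all have to be misread. It does not explain a duplicated cholesterol label either: the displaced bilirubin labels nearby are shifted, not repeated.

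**A high WBC is simply not a decrease.** Grade 0 is then the natural place for it. That is fair, and it is what a residual definition would say. The post-treatment definition says normal instead.

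**Stronger readings that the SAP does not support.**

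- *Every ungraded abnormal value strands a subject.* It does not, because the table uses the worst grade per subject.
- *Cholesterol is wrong because it has no Grade 4.* Seven other scales also end at Grade 3, so that alone shows nothing. The evidence is the repeated label.
- *Abnormal baselines of AST, ALT, ALP, GGT, bilirubin or eosinophils are misgraded as Grade 0.* Section 8.1 fixes only which measurement counts: "Baseline is defined as the last non-missing measurement collected on or before first study drug administration". The SAP does not say how that value is itself graded, so it states nothing wrong on this point. Grading baseline against ULN while keeping post-treatment grades relative to baseline would also mislead. AST unchanged at 4 x ULN, or rising to 5.6 x ULN, would print as Grade 2 to Grade 0, a false improvement that a footnote would not repair.

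**Conclusion.** The point holds for three text errors: one empty grade, one repeated grade label, and one category with two definitions. It is minor. Only descriptive shift tables are affected; the laboratory listings still show the values, as do the by-visit summaries of the quantitative tests. A reader might infer that AE severity, DLTs or dose decisions are affected too, but the SAP ties Appendix I only to the laboratory shift tables, and no such effect is shown.

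The number of subjects concerned cannot be derived from the SAP. The conclusion assumes that the printed signs and labels are those of the source file. The examples also assume the stated baselines and a WBC ULN below 15 x 10^9/L.

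**What to change.** 1. Appendix I, lymphocytes increased, Grade 2: write 4,000 < value <= 20,000/mm3, and 4 to 20 x 10^9/L in the same order, after checking the signs in the source file.
2. Appendix I, total cholesterol: reconcile the four labels with CTCAE v5.0, which the SAP adopts in section 4.1.1.
3. Section 8.4.2: define Grade 0 once for both axes as no Grade 1-4 criterion met, and do not call it normal.

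The baseline-relative grading of post-treatment values stays as it is. The cost is two corrections in the appendix and one definition in 8.4.2, with matching changes to the shift-table programs. No new data or outputs are needed. Some subjects may move to another cell in the affected tables.
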